9.11.1.3. Prospectively Enrolled Versus Retrospectively Enrolled Participants

The registry will encourage prospective registration; however, retrospective enrollment in the registry will be permitted. A prospectively enrolled participant is defined as a pregnant individual who enrolls or makes initial contact with the registry prior to pregnancy outcome. A retrospectively enrolled participant is defined as a pregnant individual who enrolls or makes initial contact with the registry after the pregnancy outcome (e.g., live birth, stillbirth, SAB, induced abortion) has occurred (up to 12-months after pregnancy outcome).

Retrospectively enrolled participants can introduce bias toward the reporting of more unusual and severe outcomes and are less likely to be representative of the general population than prospectively enrolled participants. Therefore, retrospectively enrolled participants will be excluded from the main analysis population but will be included in supplementary analyses.

Diagnostic prenatal tests (e.g., ultrasound to scan for structural defects at approximately 20 gestational weeks, chorionic villus sampling, and amniocentesis) can determine with high accuracy whether a fetus has a structural or chromosomal abnormality. Therefore, inclusion of individuals who have had diagnostic prenatal testing in the analysis population may introduce bias. To examine this potential bias, a sensitivity analysis that applies a stricter definition of prospective enrollment will be conducted. For this analysis, individuals who enroll or make initial contact with the registry prior to diagnostic prenatal testing (and pregnancy outcome) will be considered prospectively enrolled, and individuals who enroll or make initial contact with the registry after diagnostic prenatal testing, regardless of the results, will be considered retrospectively enrolled in addition to individuals who enroll after pregnancy outcome. In this sensitivity analysis, the outcomes of individuals who enroll prior to diagnostic prenatal testing will be compared with those of individuals who enrolled after diagnostic prenatal testing.

9.11.1.4. Participants Exposed to Teratogens or Investigational Medications

Participants will be considered exposed to teratogens or investigational medications during pregnancy if a dose is taken at any time during pregnancy (from conception to pregnancy outcome) or prior to pregnancy (within a specified time period based on the product's half-life). If the teratogen or investigational medication has a relatively short half-life (<3 days), participants will be considered exposed during pregnancy if a dose is taken during the period of time just prior to conception, between the first day of the LMP and the DOC. If the teratogen or investigational medication has a longer half-life, participants will be considered exposed during pregnancy if a dose is taken prior to conception within a period equivalent to 5 times the product's half-life. A list of teratogens has been developed and will be continually updated based on the data available in the Teratogen Information System (TERIS) database of teratogenic agents and recent publications.⁹³⁻⁹⁶ Participants exposed to teratogens or investigational medications during pregnancy will be excluded from the main analysis population but will be included in supplementary analyses.

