DOC, defined as 2^{0/7} gestational weeks, will be calculated as first day of LMP plus 14 days (2 weeks).

If EDD is not reported by the HCP but LMP data are available, the registry will use first day of LMP to calculate EDD, gestational age, and DOC.

Individuals will be considered exposed during pregnancy if the exposure occurs any time from 25 days prior to the DOC to the pregnancy outcome. For the analysis of MCM, first trimester exposure will be defined as exposure from 5 times the product's half-life (i.e., 25 days for tirzepatide) prior to the DOC to 13^{6/7} gestational weeks.

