9.9. Study Size

9.9.1. Sample Size

Table 9.4 presents by outcome the sample size (number of live births or pregnant individuals, depending on the outcome) required in each cohort to detect a range of relative risks, from 1.5 to 5.5. Sample size calculations were performed with SAS® statistical software (version 9.4 or higher, SAS Institute, Cary, NC) for the outcomes using the Fisher's exact conditional test with Walters normal approximation method, and assuming a power of 80%, a 2-sided α level of 0.05, an equal number of individuals in each cohort (although other sampling ratios were considered), and observed prevalence of the outcomes in the comparator cohort equivalent to reference rates in the general population. These general population rates were obtained for most (but not all) of the outcomes from various sources, including the Metropolitan Atlanta Congenital Defects Program (MACDP), the National Vital Statistics System (NVSS), and published literature.

Although the registry aims to examine a variety of maternal, fetal, and infant outcomes, the target sample size for the registry is based on the primary outcome, overall prevalence of MCM, which also is the outcome with the most restrictive denominators and one of the lowest prevalence in the general population.

As shown in Table 9.4, 265 live births in the analysis population of each cohort are needed to detect a 3-fold increase in the overall prevalence of MCM between cohorts, or a relative risk of 3.

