9.11.1. Definition of Analysis Sets

9.11.1.1. Analysis Population

As depicted in [Figure 9.2](#), the main analysis population will include participants who:

- Are valid (Section 9.11.1.1.1)
- Had a qualifying diagnosis at the time of prescribing (Section 9.11.1.1.2)
- Are prospectively enrolled (Section 9.11.1.1.3)
- Are not exposed to teratogens or investigational medications or congenital infectious agents during pregnancy (Section 9.11.1.1.4)
- Are not considered lost to follow-up (Section 9.11.1.1.5)
- Are not already included in the analysis population for a prior pregnancy (Section 9.11.1.1.6), and
- Among the tirzepatide exposed cohort, have not been exposed to other GLP-1 RA therapies during pregnancy or within 5 times the half-life of the drug prior to conception.

For the analyses of preterm birth, SGA, postnatal growth deficiency, rapid infant weight gain, and infant developmental delay, multiple gestation pregnancies will be excluded from the analysis population.

Abbreviation: HCP = healthcare professional; GLP-1 RA = glucagon-like peptide-1 receptor agonist.

Figure 9.2. Attrition diagram.

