9.11.2.1. Analysis of Primary Outcome

Prevalence of the primary outcome will be calculated according to the conventions described in [Table 9.6](#). In general, prevalence will be calculated by dividing the number of cases with an MCM by the appropriate denominator. Prevalence is preferred over incidence when examining pregnancy outcomes, such as congenital malformations, because incidence cannot be reliably estimated given the complexities in the reproductive process.⁹⁷

For MCM, prevalence in the exposed cohort will be calculated among the subset of individuals who are exposed during the first trimester. For the primary analysis, prevalence will be calculated among live births, and a secondary analysis will be conducted among live births and fetal losses ([Table 9.6](#)).

The unweighted univariate regression will be used to compare the crude (unadjusted) relative risks (RRs) of MCM in the tirzepatide exposed and each of the comparator groups, respectively: tirzepatide exposed vs. AOM active comparator and tirzepatide exposed vs. AOM unexposed comparator.

Adjusted methods will incorporate weights estimated using the inverse probability of treatment weighting (IPTW) method to balance the cohorts regarding observable covariates. A weighted generalized linear model using a binomial family and a log (RR) link with robust sandwich variance estimation or a modified Poisson regression⁹⁸ with robust error variance will be employed to estimate an adjusted RR. As with the unweighted analysis, two sets of comparisons will be conducted separately: tirzepatide vs. AOM active comparator and tirzepatide vs. AOM unexposed comparator.

The adjusted comparison of the overall prevalence of MCM observed in the tirzepatide exposed and the comparator cohorts will be considered the primary analysis. A p-value <0.05 will be considered statistically significant.

Table 9.6. Calculation of Primary Outcome Prevalence

Outcome	Numerator	Denominator
Primary analysis: among live births	Live births with confirmed (by adjudication) MCMs (excluding MCMs not known to be associated with medication exposure ^a) among individuals with pregnancy outcome data and, if applicable, exposure during 1 st trimester	Live births among individuals with pregnancy outcome data and, if applicable, ^b exposure during 1 st trimester

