9.11.2.2. Analysis of Secondary and Exploratory Outcomes

Prevalence of the secondary and exploratory outcomes will be calculated according to the conventions described in [Table 9.7](#). In general, the prevalence of each outcome will be calculated by dividing the number of cases of the outcome by the appropriate denominator for that particular outcome, based on clinical knowledge.

Table 9.7. Calculation of Secondary and Exploratory Outcome Prevalence

Outcome [Exposure window]	Numerator	Denominator
Secondary outcomes		
Maternal pregnancy complications		
Gestational diabetes [Exposure: Any trimester]	Individuals with gestational diabetes	Individuals included in the analysis population
Sensitivity analysis: Gestational diabetes	Gestational diabetes among pregnancies with pregnancy outcome data	Individuals with pregnancy outcome data
Pregnancy-induced hypertension [Exposure: Any trimester]	Individuals with pregnancy-induced hypertension	Individuals with pregnancy of 20 gestational weeks or more
Sensitivity analysis: Pregnancy-induced hypertension	Pregnancy-induced hypertension among pregnancies with pregnancy outcome data	Individuals with pregnancy of 20 gestational weeks or more with pregnancy outcome data
Pre-eclampsia [Exposure: Any trimester]	Individuals with pre-eclampsia	Individuals with pregnancy of 20 gestational weeks or more
Sensitivity analysis: Pre-eclampsia	Pre-eclampsia among individuals with pregnancy outcome data	Individuals with pregnancy of 20 gestational weeks or more and with pregnancy outcome data
Eclampsia [Exposure: Any trimester]	Individuals with eclampsia	Individuals with pregnancy of 20 gestational weeks or more
Sensitivity analysis: Eclampsia	Eclampsia among individuals with pregnancy outcome data	Individuals with pregnancy of 20 gestational weeks or more with pregnancy outcome data
Fetal Outcomes		
SAB [Exposure: DOC to $\leq 19^{6/7}$ gestational weeks]	SABs among individuals with pregnancy outcome data who are enrolled (and exposed, if applicable) prior to 20 gestational weeks	Individuals with pregnancy outcome data who are enrolled (and exposed, if applicable) prior to 20 gestational weeks
Induced abortion [Exposure: Any trimester]	Individuals with pregnancy ending in induced abortions	Individuals included in the analysis population
Sensitivity analysis: Induced abortion	Induced abortions among individuals with pregnancy outcome data	Individuals with pregnancy outcome data

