- Sensitivity analyses will also be conducted to assess the potential impact of missing data and/or unmeasured confounding (e.g., quantitative bias analysis to estimate the overall strength of potential unmeasured confounding required to nullify the estimated treatment effect or reverse the statistical inference).¹⁰⁸
- A sensitivity analysis will be conducted that limits the tirzepatide exposed and the AOM active comparator cohorts to individuals with a diagnosis of obesity, or overweight with at least one weight-related comorbid condition at the time of conception.
- A sensitivity analysis will be conducted that expands the tirzepatide exposed cohort to individuals exposed to any other weight loss medications (including GLP-1 RAs) other than tirzepatide.
- In the main analysis, maternal use of within 5 half-lives of the respective medication is defined as a potential fetal exposure to medication use during pregnancy. This is a conservative estimate which may dilute a potential association between medication and the study outcomes. Sensitivity analysis will be conducted with shorter half-lives (i.e., 1-, 2- and 3-times half-lives) to define fetal exposure to medication use during pregnancy.
- Pregnant individuals who are exposed to a known teratogen or an investigational medication during or prior to pregnancy will be excluded from the main analysis population and described in the supplementary analyses. In the case that there are more than 10% of pregnant individuals with teratogen exposure during or prior to pregnancy, an additional sensitivity analysis will be considered by retaining those individuals in the analysis and addressing potential impact of teratogen exposure via analytical adjustment. More details will be included in the SAP.

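### The teratogen and investigational-drug exclusion runs to pregnancy outcome for every endpoint, so a drug given because of a complication or loss can remove the woman and her event from the main analysis.

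*Protocol*

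**What the plan says.** The section on participants exposed to teratogens or investigational medications (headed 9.11.1.4 in the text, cited elsewhere as 9.11.1.1.4) treats a woman as exposed "if a dose is taken at any time during pregnancy (from conception to pregnancy outcome", or within a pre-conception window that depends on half-life. The consequence is: "Participants exposed to teratogens or investigational medications during pregnancy will be excluded from the main analysis population but will be included in supplementary analyses".

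Section 9.11.1.1 makes this a membership criterion of the single main analysis population: "Are not exposed to teratogens or investigational medications or congenital infectious agents during pregnancy". It is not tied to an outcome. In Table 9.7 the denominators for gestational diabetes, induced abortion, stillbirth and several exploratory outcomes are "Individuals included in the analysis population", so they inherit it directly; the other rows are further restrictions of the same population.

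Excluded women return in two places. Section 9.11.2.6 brings them back in supplementary analyses that it calls descriptive. Section 9.11.2.7 foresees an adjusted analysis that retains them, but only as something to be considered and only on a condition: "In the case that there are more than 10% of pregnant individuals with teratogen exposure during or prior to pregnancy". Investigational drugs do not count towards that condition.

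**The concern.** The exclusion depends on something that happens after enrolment, and it has no before-event limit and no exception for a drug given because of the outcome. An investigational or listed drug given to treat a complication, or to manage or end the pregnancy, is still a dose before pregnancy outcome. The case is then deleted because it was a case.

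Table 9.3 lists the teratogen exclusion under malformation analyses, where its purpose is clear. Sections 9.11.1.1 and 9.11.1.4 extend it to all outcomes without a reason specific to gestational diabetes, hypertensive disorders, fetal loss or preterm birth. Elsewhere the plan does work by outcome: loss to follow-up, multiple gestations, and the study-drug windows for spontaneous abortion and preterm birth.

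Two things are at stake. The secondary objective is to describe prevalence as well as compare it, and prevalence would be too low. The RR would also be biased if treatment after an event differs by cohort. Weighting on baseline covariates (Section 9.11.2.4) cannot repair selection that depends on the outcome.

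**Working it through.** **1. The plan's own figure.** Section 9.9.1 gives 265 live births per cohort, "assuming a power of 80%, a 2-sided α level of 0.05, an equal number of individuals in each cohort", with malformation prevalence of 3% against 9% (RR 3). The named method (Walters approximation to Fisher's exact test) is

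power = Φ(√(2n)·[asin√(p1 − 1/(2n)) − asin√(p0 + 1/(2n))] − 1.96).

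With n = 265, p0 = 0.03 and p1 = 0.09, power is 80.1%. Then 265/0.9³ = 363.5, rounded up to 364 per cohort; 3 × 364 = 1,092. The plan's figures reproduce.

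**2. Does the rule cost malformation power?** One factor of 0.9 in that formula is the exclusion allowance, and it names teratogen, investigational-drug and infection exposure. Of the 10%, 5% is loss to follow-up, leaving at most 5% for all other reasons together.

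- As planned: 364 × 0.81 × 0.90 = 265 live births, power 80.1%.
- If the whole remaining 5% were late-only exposure and were kept: 364 × 0.81 × 0.95 = 280, power 82.5%.

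So the most that could be gained is about 15 live births per cohort (280 − 265). There is no shortfall against plan.

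**3. Event deletion.** Let p be the true prevalence and d the share of cases removed. Cases leave numerator and denominator together, so the observed prevalence is p(1 − d)/(1 − pd). For pre-eclampsia at 3.8% (Table 9.4), with d assumed:

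| d | observed prevalence |
|---|---|
| 10% | 3.4% |
| 25% | 2.9% |
| 50% | 1.9% |

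For a true RR of 1.5 (3.8% against 5.7%), the observed RR is the ratio of the two adjusted prevalences:

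| removed, tirzepatide | removed, comparator | observed RR |
|---|---|---|
| 25% | 25% | 1.51 |
| 50% | 50% | 1.52 |
| 25% | 10% | 1.26 |
| 50% | 25% | 1.02 |
| 10% | 25% | 1.79 |

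Prevalence falls in every row. The RR moves materially only when removal differs, and it can move either way.

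**4. Would the retaining analysis be triggered?** It needs more than 10% with teratogen exposure. The sample-size allowance leaves at most 5% for every exclusion other than loss to follow-up. If exclusions run as planned, the condition is never met. It also depends on how common exposure is, not on whether events are being selectively removed.

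**The case against.** **The list.** Which drugs trigger the exclusion is set by a standalone List of Known Teratogens (Annex 1), which is not shown. A reader might infer that common obstetric treatments are on it and that events will be lost routinely. The protocol does not say so, and the list might carry timing limits. This stands as a limit on frequency. It does not remove the mechanism: investigational drugs trigger the exclusion whatever the list contains.

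**Power.** A reader might infer that late doses shrink the malformation set below 265, for example to 238 with 75.1% power if a further 10% were lost. That subtracts from a figure already net of exclusions. Section 9.9.1 also says that enrolment into the main population will be assessed throughout and mitigation considered if exclusions run high.

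**Bias factor.** The shortcut (1 − x1)/(1 − x0), with x1 and x0 the shares of tirzepatide and comparator events removed, ignores the denominator. For induced abortion at 18.6%, RR 1.5 and removal of 30% against 10%, it gives 0.78. Adjusting the denominators gives 0.2131/0.1706 = 1.25, a factor of 0.83. The documents also give no reason to expect removal to differ by cohort.

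**Malformation window.** For the study drug, "prevalence in the exposed cohort will be calculated among the subset of individuals who are exposed during the first trimester", and Section 9.7.5 fixes that window. A reader might infer that the teratogen window should be cut to match. But Table 9.3 defines major malformations by structure or function, and Table 9.7 gives minor malformations an any-trimester window. The documents do not support the cut.

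**Existing safeguards.** Section 9.11.2.3 compares included with excluded women, and Sections 9.11.2.6 and 9.11.2.7 bring excluded women back. These soften the point. None guarantees an adjusted comparison with the removed events restored.

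**Conclusion.** The point holds for outcomes other than malformations. The protocol fixes an exclusion that can follow from the event itself, and it applies to the main analysis of maternal complications, fetal losses and preterm birth. Prevalence is understated by an amount that cannot be established from the protocol; at assumed removal of 10% to 50% of cases, pre-eclampsia at 3.8% would be observed as 3.4% to 1.9%. The RR is almost unchanged under equal removal and biased in either direction under unequal removal. No loss of malformation power against plan is shown. The point is worth correcting because this is a safety registry and the repair is cheap, not because a large bias has been demonstrated.

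**What to change.** 1. For outcomes other than malformations, base the exclusion on teratogen or investigational exposure dated up to registry enrolment, with the same cut-off for women with and without the event. A cut at the event date would not do: cases would be excludable only until onset and non-cases throughout pregnancy, which is a new outcome-dependent exclusion.
2. State that a drug given to treat, manage or bring about the outcome does not trigger exclusion. This is needed alongside the cut-off because a complication can precede enrolment.
3. Run the adjusted sensitivity analysis that retains these women whatever the percentage exposed, and include investigational drugs in it.
4. Leave the malformation window as it is, and examine late-only exposures in that sensitivity analysis.

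The cost is wording and one unconditional analysis. Section 9.8 already collects dates and reason for use, where available. The downside is that a few women with later teratogen or investigational exposure stay in the main analysis of non-malformation outcomes. The window will also vary with gestational age at enrolment, which Section 9.7.4 already lists as a potential covariate.

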9.11.1.1.5. Participants Lost to Follow-up

A participant will be considered lost to follow-up if follow-up information is never obtained or is unavailable; pregnant individuals without pregnancy outcome information will be considered lost to follow-up for pregnancy outcome, and live-born infants without follow-up data after birth will be considered lost to follow-up. Lost to follow-up is considered by outcome and participants are eligible to be included in calculation of all outcomes they contributed to up to the point of loss to follow-up (e.g., if pregnancy complications were observed prior to a maternal death, any observed complications as well as the pregnancy outcome would be captured and included in analyses, but after that point the case would be considered lost to further follow-up). Section [9.6.1](#) provides more information on the circumstances under which participants will be considered lost to follow-up. Information from these participants (e.g., baseline characteristics, abnormal prenatal test results, and reason for loss to follow-up, if available) will be summarized in each registry report, but these participants will be excluded from the main analysis population.

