Stillbirth [Exposure: Any trimester]	Individuals with pregnancy ending in stillbirth	Individuals included in the analysis population
Sensitivity analysis: Stillbirth	Stillbirths among individuals with pregnancy outcome data	Individuals with pregnancy outcome data
Infant Outcomes		
Minor congenital malformations [Exposure: Any Trimester]	Live births with minor congenital malformations among individuals with pregnancy outcome data	Live births among individuals with pregnancy outcome data
Preterm birth [Exposure: DOC to < 37 weeks gestation]	Singleton preterm live births without MCMs among individuals with pregnancy outcome data who are enrolled (and exposed, if applicable) prior to 37 gestational weeks	Singleton live births without MCMs among individuals with pregnancy outcome data who are enrolled (and exposed, if applicable) prior to 37 gestational weeks

Outcome [Exposure window]	Numerator	Denominator
SGA [Exposure: Any trimester]	Singleton live births who are SGA at birth among individuals with pregnancy outcome data	Singleton live births among individuals with pregnancy outcome data
Sensitivity analysis: SGA	Singleton live births without MCMs who are SGA at birth among individuals with pregnancy outcome data	Singleton live births without MCMs with weight data among individuals with pregnancy outcome data
Postnatal growth and development outcomes		
Postnatal growth deficiency (at 4 and 12 months) [Exposure: Any trimester]	Singleton infants with postnatal growth deficiency based on weight/length/head circumference among infants with weight/length/head circumference data at the time point	Singleton infants with follow-up data at the time point
Sensitivity analysis: Postnatal growth deficiency (at 4 and 12 months)	Singleton infants without MCMs who were not born preterm or SGA with postnatal growth deficiency based on weight/length/head circumference among infants with weight/length/head circumference data at the time point	Singleton infants without MCMs who were not born preterm or SGA with weight/length/head circumference data at the time point
Infant developmental delay (at 4 and 12 months) [Exposure: Any trimester]	Singleton infants with developmental delay in a particular category among infants with developmental milestone data for the category at the time point	Singleton infants with follow-up data at the time point

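### The lost-to-follow-up rule contradicts itself, so the main stillbirth and induced abortion rows either count unknown outcomes as non-events or are repeated by their sensitivity rows

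*Protocol*

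**What the plan says.** Four places in the Protocol bear on this point.

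- **Section 9.11.1.1.5 (Participants Lost to Follow-up)** defines the loss: "pregnant individuals without pregnancy outcome information will be considered lost to follow-up for pregnancy outcome". It then says "Lost to follow-up is considered by outcome and participants are eligible to be included in calculation of all outcomes they contributed to", limited to the time before loss, and gives as its example complications seen before a maternal death. Its last sentence says that information on lost participants will be summarized, "but these participants will be excluded from the main analysis population".
- **Section 9.11.1.1 (Analysis Population)** lists not being lost to follow-up as a condition for entering the main analysis population, with no qualification by outcome.
- **Section 9.9.1 (Sample Size)** counts lack of pregnancy outcome data, assumed at 5%, within the 10% of enrolled individuals excluded from the analysis population.
- **Table 9.7 (section 9.11.2.2)** defines the main stillbirth numerator as "Individuals with pregnancy ending in stillbirth" and the main induced abortion numerator as "Individuals with pregnancy ending in induced abortions". Both have the denominator "Individuals included in the analysis population". Each has a sensitivity row restricted to individuals with pregnancy outcome data. The main spontaneous abortion row already carries that restriction, as do the MCM rows in Table 9.6.

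**The concern.** Stillbirth, induced abortion, spontaneous abortion and live birth are mutually exclusive categories of one variable (section 9.8). A woman whose pregnancy outcome is unknown therefore has no value for any of them. The protocol requires a known outcome for spontaneous abortion but not, in the main rows, for stillbirth or induced abortion.

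Both the population rule and the denominators are fixed in the protocol, so this is not a detail waiting for the SAP. Two programmers following the text could build different main tables. On one reading the main prevalences are diluted by women who can never enter the numerator. On the other, the sensitivity analysis meant to probe this cannot give a different answer. Section 9.13 concedes that outcomes in lost women could differ from documented ones and that the impact cannot be assessed with certainty, so a sensitivity row that does nothing is a real gap.

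**Working it through.** **Inputs, all from the Protocol**
- Enrolment of 364 per cohort, total exclusions of 10%, and 5% lost to follow-up within that 10% (section 9.9.1). The 5% is read here as a share of those enrolled.
- Reference prevalence of 0.596% for stillbirth and 18.6% for induced abortion (Table 9.4). Their source denominators are births rather than all pregnancies, so they serve only as illustration. The relative change below does not depend on them.

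**Plan's own figure.** 265 / 0.9 / 0.9 / 0.9 = 363.5, rounded up to 364 per cohort; 3 × 364 = 1,092. Both figures reproduce.

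**Reading A: women without a pregnancy outcome are excluded from the population** (sections 9.9.1 and 9.11.1.1, and the last sentence of 9.11.1.1.5)
- Main denominator: 364 × 0.90 = 327.6, about 328.
- Sensitivity denominator: everyone left has a pregnancy outcome, so the same 328.
- The rows cover the same women.

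**Reading B: strictly by outcome**
- A woman lost for pregnancy outcome leaves the pregnancy-outcome rows but stays in rows for events observed earlier.
- For stillbirth and induced abortion the main and sensitivity sets again coincide.

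**Reading C: such women stay in the main denominator** (the only reading on which the two Table 9.7 denominators differ)
- Women with unknown outcome: 364 × 0.05 = 18.2.
- Main denominator: 327.6 + 18.2 = 345.8, about 346. Share unknown: 18.2 / 345.8 = 5.3%.
- Factor on prevalence: 327.6 / 345.8 = 0.947.
- Stillbirth: 0.596% × 0.947 = about 0.565%.
- Induced abortion: 18.6% × 0.947 = about 17.6%.

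**Effect on the relative risk under Reading C.** With unknown shares L_t (tirzepatide) and L_c (comparator) of the main denominator, the factor is (1 − L_t) / (1 − L_c). Unequal shares are an assumption; the protocol gives none.

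| L_t | L_c | Factor on RR |
|---|---|---|
| 5% | 5% | 1.00 |
| 5% | 10% | 0.95/0.90 = 1.06 |
| 10% | 5% | 0.90/0.95 = 0.95 |
| 5% | 15% | 0.95/0.85 = 1.12 |
| 15% | 5% | 0.85/0.95 = 0.89 |

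No reading gives main rows for these two outcomes that are both free of unknown outcomes and different from their sensitivity rows. One small caveat: the main numerators count individuals and the sensitivity numerators count events, so a multiple pregnancy could make a trivial difference even when the women are the same.

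**The case against.** The strongest reply is that the text can be reconciled. Loss is judged by outcome, and eligibility runs only up to the point of loss. A woman with no known pregnancy outcome contributed nothing to stillbirth or induced abortion and so drops out of those rows. The closing sentence of section 9.11.1.1.5 can then be read as exclusion for the outcome concerned. On that view nothing is biased and only redundancy remains. Much of this stands: it is the most natural repair, and it makes Reading C the least supported. But the closing sentence and the section 9.11.1.1 criterion are unqualified as written, and Table 9.7 words the two denominators as if they differed.

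A reader might infer that the planned relative risks for these outcomes are biased. The protocol does not support that. It would take both Reading C and unequal loss, while the only loss figure given is 5%. Data collection is to be identical across cohorts (sections 9.6 and 9.13), lost participants are compared with those analysed (section 9.11.2.3), and section 9.11.2.7 plans missing-data sensitivity analyses in general terms.

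A reader might also extend the point to gestational diabetes and the hypertensive complications, which have similar row pairs. That does not follow. Those events can be observed before loss, so under a by-outcome rule the main and sensitivity rows differ and the comparison is informative. They become redundant only under blanket exclusion. Nor are the present main rows an all-enrolled analysis: the analysis population already excludes invalid, retrospectively enrolled and teratogen-exposed participants, among others.

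Finally, the consequences are limited. Both outcomes are secondary with nominal p-values (section 9.11.2), and stated power for a three-fold increase in stillbirth is 21.4% (Table 9.5).

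**Conclusion.** The point holds as an internal contradiction affecting two secondary outcomes. The protocol both keeps lost women by outcome and says "these participants will be excluded from the main analysis population", and Table 9.7 fits neither rule for stillbirth and induced abortion. The consequence is one of two things:

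- about 18 of 346 women per cohort counted as event-free with unknown outcome, lowering prevalence by about 5% in relative terms; or
- two sensitivity rows that repeat their main rows.

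The first size rests on the protocol's own 5% and 10% assumptions. Any shift in the relative risk is conditional on differential loss, which is assumed here and not documented. The primary MCM analysis and the spontaneous abortion row require pregnancy outcome data and are not touched. It should be corrected, but it does not threaten the study's main conclusion.

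**What to change.** 1. In sections 9.11.1.1 and 9.11.1.1.5, state one rule: a woman is excluded only from the outcomes to which she was not followed. Qualify the inclusion criterion and the closing sentence accordingly.
2. In Table 9.7, make individuals with pregnancy outcome data the main denominator for stillbirth and induced abortion, as for spontaneous abortion.
3. Replace their sensitivity rows with ones that change how unknown outcomes are handled, for example the analysis population with women lacking pregnancy outcome data added back.
4. Leave the main rows for gestational diabetes, pregnancy-induced hypertension, pre-eclampsia and eclampsia as they are. Under the by-outcome rule their sensitivity rows become informative.

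The cost is a few sentences and two pairs of table rows. No new data are needed, and the sample size does not change, because the MCM analysis already requires pregnancy outcome data.
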